14. STATISTICAL CONSIDERATIONS

A separate Statistical Analysis Plan (SAP) will be produced and will provide a more comprehensive description of the planned statistical analyses. All participants will be analysed according to the duration they were randomly assigned to, regardless of adherence to the treatment protocol. A brief overview of the planned analyses is provided here.

14.1 Sample size

We aim to randomise 705 children in a 1:1:1:1:1 ratio to receive either 3, 5, 6, 8 or 10 days of cefalexin. We estimate that this will provide us with 500 patients (100 in each duration) for our microbiological population. The "DURATIONS design" estimates that a sample size of 500 patients divided into a moderate number of broadly equidistant arms (5–7 arms) is required to estimate the duration—response curve satisfactorily (29). Simulations based on plausible scenarios showed that such a sample size was enough to estimate the curve within 5% average absolute error in 95% of simulations. Power for the optimal duration analysis is dependent on the assumed shape of the response curve. We will task the DMC with assessing a more accurate simulation of the analysis at the end of the internal pilot period (using concurrent data) to ascertain if our sample size assumptions remain robust, or whether we require a larger sample size.

Analysis in both the microbiological-confirmed population (those with proven UTI who are not resistant to cefalexin) and the intention-to-treat (ITT) population will be carried out. Given that randomisation occurs before urine culture results are known, the number of patients not included in the microbiological-confirmed population should be equally distributed between treatment arms, thus limiting risk of bias.

Of the population it is estimated that:

- ~12% of participants will not have a proven UTI on urine culture, despite initial clinical symptoms and/or positive point-of-care test (information estimated from a local audit of 530 urine culture results at Birmingham Children's Hospital, 95% CI 9.3% 14.9%).
- ~10% of proven UTIs (8.8% of entire population) involve a cefalexin-resistant pathogen (10).
- ~10% will be lost to follow up.

Therefore, it is estimated that a sample size of 705 is needed to ensure that at least 500 participants are in the microbiological-confirmed population. For the ITT population, assuming a loss to follow up of 10%, 705 participants will provide 634 participants for analysis. These assumptions will be closely monitored during the trial and, should the number of participants excluded from the microbiological-confirmed analysis be higher than our estimates, then adjustments to the recruited sample size will be made to ensure 500 for this analysis. Conversely, if the number of participants excluded from the microbiological-confirmed analysis is lower than our estimate, we will continue to recruit to a total of 705 participants, with the aim of increasing precision around our estimates. As our estimates are likely to be close to the actual numbers, any adjustment will be modest and unlikely to have major impacts on trial duration, given the expected rapid recruitment to this trial.

14.2 Primary analysis

In line with recommendations from the European Medicines Agency (32, 34), the primary analysis will be conducted on the microbiological-confirmed population.

The microbiological-confirmed population is defined as: All randomised patients who have a baseline bacterial pathogen on culture of urine that causes UTI against which cefalexin has antibacterial activity. As in clinical practice, a culture-positive UTI will be defined using the following thresholds (32):

Either:

(i) Pure growth of a single organism recognised as pathogenic for UTI with the following colony count:

- ≥100,000/ml (clean catch urine or midstream urine)
- ≥10,000/ml (catheter urine or suprapubic aspirate)

or

(ii) Growth of no more than 2 organisms. One predominant organism recognised as pathogenic for UTI with the following colony count:

- ≥100,000/ml (clean catch urine or midstream urine)
- ≥10,000/ml (catheter urine or suprapubic aspirate)

The trial sample size (Section 14.1) has been calculated to ensure sufficient participants for this microbiological-confirmed population.

14.3 Secondary Analysis

A secondary analysis will be performed on all randomised patients i.e. the ITT population, including those who do not have proven UTI, and those who have a cefalexin-resistant pathogen. This will be conducted using a series of assumptions regarding successful cure and failure to cure:

(i) **Cefalexin-resistant UTI**: The participants outcome will be classified as failure to cure, given that the causative organism is not susceptible to effective treatment by cefalexin. Sites will be responsible for ensuring that these participants receive an appropriate change of antibiotic and any necessary imaging and follow-up, in line with their standard local clinical practice.

(ii) **No growth in baseline urine culture**: The participants outcome will be classified as successful cure, given that, by definition, they do not have an untreated-UTI at the point of primary outcome assessment.

(iii) **Below threshold growth in baseline urine culture**: For the same reason as for (ii), the participant outcome will be classified as successful cure.

(iv) **Contamination (mixed growth) in baseline urine culture**: These participants will undergo the standard primary outcome assessment, as for the microbiological-confirmed population. Standard clinical practice will ensure that these participants receive additional investigation and/or change of antibiotic if this is clinically warranted.

(v) **Baseline urine culture result missing**: These participants will undergo the standard primary outcome assessment, as for the microbiological-confirmed population.

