Interventions: Patients will be randomised to one of five cefalexin course durations (3, 5, 6, 8 or 10 days). Patients will be allocated to groups using central randomisation in a 1:1:1:1:1 ratio with minimisation to ensure balance for age group, sex and study site. Cefalexin will be administered as a standard proprietary liquid suspension at a dose in line with current recommendations of the British National Formulary for Children (BNFC).

Outcome measures:

Primary outcome: Clinical UTI cure, defined as patients in whom there is (i) fever resolution and (ii) no additional systemic antibiotic prescription by 16 days post-randomisation.

Secondary outcomes:

- UTI recurrence (relapse or reinfection), up to final follow-up, 30 days post-randomisation
- Fever resolution at the primary outcome assessment visit (16 days post-randomisation)
- Producing a sterile urine at the primary outcome assessment visit (16 days postrandomisation)
- No additional systemic antibiotic prescription by the primary outcome assessment visit (16 days post-randomisation)
- Antibiotic-associated adverse events (including diarrhoea, rashes, and candida infections) up to 30-day follow-up
- Adherence to trial medication (no more than 1 missed dose and no additional doses)
- Antimicrobial resistance, determined from a comparison of the antibiotic sensitivities of preand post-treatment urine samples along with the identification of extended-spectrum betalactamase (ESBL)-producing organisms
- Differences in quality of life (using the Child Health Utility instrument CHU9D) between the different treatment duration arms.

Follow-up: To 30 days post-randomisation.

Health economics: An incremental cost-utility analysis will determine the cost-effectiveness of the different treatment durations over the follow-up period.

Analysis: Duration-response curves will be generated for both the microbiological-confirmed and intention-to-treat (ITT) cohorts using fixed-2 fractional polynomial models. These curves will then be used to estimate the minimum duration of cefalexin, to ensure that at least 90% of the efficacy provided by the maximum length (10 day) course of antibiotics is achieved.

TRIAL SCHEMA

Figure 1: Randomisation, study populations and outcomes

TABLE OF CONTENTS

Trial Schema
Randomisation, study populations and outcomes14
Trial activities

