9. TRIAL PROCEDURES

9.1 Schedule of assessments

The frequency of follow-up visits and assessments are detailed in the **Schedule of Assessments** (Table 4).

Trial visits and contact schedules should be determined and assigned for each child at randomisation, and children should be followed on that schedule, until the final follow-up visit, even if their trial medication is discontinued prematurely. The schedule defines visit dates (with windows) necessary for data collection.

The face-to-face ED follow-up for the primary outcome assessment will be scheduled in advance, ideally at 16 days post-randomisation, but with a window of ±2 days to allow for weekends and public holidays. If the visit is missed without notice, the research team will endeavour to contact the parent/guardian by phone. If the primary outcome follow up can only be conducted by phone, the parent/guardian will be encouraged to provide a sample of their child's urine remotely.

During any unscheduled acute events, the child can be seen face-to-face if attending the randomising centre. Otherwise, a telephone contact can be arranged.

Table 4: Schedule of Assessments

Day of Trial	dO	d0	d0-d10	48-72 hrs post- cefalexin completion	d16 (±2d)	d30 (±2d)	Any
Visit	Screening	Baseline	Monitoring via CURLY app	Fit & well check	Primary outcome assessment	Recurrence follow-up	Any acute event
At site/remote	Site	Site	Remote	Remote	Site	Remote	Either
Point-of-care dipstick urinalysis	х				x		(X)
Urine sample sent for culture, microscopy & antibiotic sensitivity	х				x	х	(X)
Eligibility check	х						
Valid informed consent/assent		х					
Relevant medical history taken		х					
Documentation of relevant physical examination findings		х			(X)	(X)	(X)
Symptom checklist		Х	х	х	х	х	(X)
CHU9D questionnaire		Х			х	х	
Randomisation		Х					
Allocation of trial number		х					
Cefalexin prescription & dispensing		х					
Setup of CURLY app		Х					
Education/advice to parent/guardian		х					
Concomitant medications			х		х	х	
Log of administration of cefalexin doses			x				
Adverse event reporting			х	х	х	х	х
Reminder text/email on final day of cefalexin			x				
Health resource use questionnaire				х	х	х	х
Stool sample or rectal swab					(X)*		

 $(X)^* = Optional sample collection participants only (after optional consent)$

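### The ITT curve scores children with no growth or below-threshold growth as cured whatever their day-16 outcome, which contradicts the endpoint and tends to favour shorter courses

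*Protocol*

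**What the plan says.** Section 14.3 defines a secondary analysis on all randomised patients, called ITT, and sorts them by baseline culture.

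- Resistant pathogen: "The participants outcome will be classified as failure to cure".
- No growth: "The participants outcome will be classified as successful cure, given that, by definition, they do not have an untreated-UTI".
- Below-threshold growth, for the same reason: "the participant outcome will be classified as successful cure".
- Mixed growth, or no culture result: the standard day-16 assessment is used.

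The Trial Summary gives this cohort the same treatment as the primary one: "Duration-response curves will be generated for both the microbiological-confirmed and intention-to-treat (ITT) cohorts". Section 14.4 then derives from each curve the optimal duration D*, the shortest that keeps at least 90% of the 10-day cure rate.

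Sections 8.1 and 14.4 define cure by two clinical facts at day 16: the fever has resolved, and no additional systemic antibiotic has been prescribed. Baseline culture is not part of the definition. On follow-up, Section 9.1 says "children should be followed on that schedule, until the final follow-up visit, even if their trial medication is discontinued prematurely", and Section 9.6 adds telephone and GP contact when the visit is missed.

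**The concern.** The reason given for scoring these children as cured is that they have no untreated infection. The endpoint does not ask that. A child with no growth at baseline can still be febrile at day 16, or can have been given another antibiotic, and is then a failure as defined. Section 14.3 counts that child as a cure and overrides an outcome the trial plans to collect.

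An outcome fixed at baseline also cannot vary with duration. If culture-negative children do differ between arms, the ITT curve cannot show it. That is possible in an open-label trial where further prescribing is at the clinician's discretion (Sections 6.5 and 7.5).

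Treatment is chosen before the culture is known, so the ITT curve is the one that should describe what happens when a duration is prescribed in the emergency department. Section 14.7 lists a per-protocol analysis, missing-data assumptions and a urine-sterilisation variant, but no version of the composite based on observed outcomes in all randomised children.

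**Working it through.** **Inputs (Section 14.1).** "We aim to randomise 705 children in a 1:1:1:1:1 ratio to receive either 3, 5, 6, 8 or 10 days of cefalexin"; "12% of participants will not have a proven UTI on urine culture", with an audit confidence interval of 9.3% to 14.9%; 10% of proven UTIs resistant; 10% lost to follow-up.

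**The plan's own figures reproduce.** Resistant share: 0.88 × 0.10 = 8.8%. Microbiological-confirmed: 705 × 0.88 × 0.90 × 0.90 = 502.5, against a target of 500. ITT: 705 × 0.90 = 634.5, against "705 participants will provide 634 participants for analysis".

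**How many are scored as cured.** At most 0.12 × 705 = 85 (66 to 105 over the audit interval), or 0.12 × 634 = 76. Any mixed-growth or missing-culture children within the 12% keep their observed outcome. If they were half of it (assumption), the 76 would be 38.

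**Failures recoded.** The documents give no failure rate for these children. At 5% to 20% (assumption), 85 × 0.05 to 85 × 0.20 = 4 to 17, or about 1 to 3 per arm.

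**Effect on the 90% criterion.** Let p(d) be cure in susceptible proven UTI (share 1 − 0.12 − 0.088 = 0.792) and q(d) be observed cure in the 12%. Resistant children count as failures in both versions.

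- Under the rule: 0.12 + 0.792 p(d)
- Observed: 0.12 q(d) + 0.792 p(d)

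The margin at duration d is the curve minus 0.9 times its 10-day value. The rule's margin minus the observed margin is

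0.12 × [0.1 × (1 − q(10)) + (q(10) − q(d))].

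The first term comes from the level of cure and is small. The second is the duration effect that the rule removes. The sum is positive, so the criterion is easier, unless q(d) exceeds q(10) by more than a tenth of the 10-day failure rate.

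- q flat at 0.90: 0.12 × 0.01 = 0.12 percentage points.
- q(3) = 0.85, q(10) = 0.95: at day 3, 0.12 × (0.005 + 0.10) = 1.3 points.
- q(3) = 0.75, q(10) = 0.95: at day 3, 0.12 × (0.005 + 0.20) = 2.5 points.

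**Effect on D\*.** The documents give no cure rates, so all curves are assumed. p and q both rise from day 3 to day 10 in proportion to 1 − exp(−k(d − 3)). D* in days:

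| p(3), p(10), k | Rule | Observed, q flat 0.90 | Observed, q 0.85 to 0.95 | Observed, q 0.75 to 0.95 |
|---|---|---|---|---|
| 0.80, 0.95, 0.5 | 3.60 | 3.62 | 3.79 | 3.96 |
| 0.70, 0.95, 0.4 | 4.86 | 4.89 | 5.01 | 5.13 |
| 0.60, 0.95, 0.3 | 6.07 | 6.10 | 6.18 | 6.27 |
| 0.75, 0.90, 0.3 | 4.02 | 4.06 | 4.30 | 4.54 |

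The rule shortens D* by 0.02 to 0.04 day when q is flat and by 0.11 to 0.52 day when q rises with duration. These use the full 12% and are therefore upper figures for each assumed curve.

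**The case against.** The rule is pre-specified, openly labelled as a set of assumptions, and confined to a secondary analysis. It also has a clinical argument. A child without a urinary infection has no UTI to fail, and fever or antibiotics for another illness would otherwise count as failed UTI cure. Section 7.4 lets sites stop cefalexin after a negative culture, so day-16 results in these children may not reflect the allocated duration. This makes the assigned version a defensible sensitivity analysis. It does not make it the observed endpoint in all randomised children, which is what the ITT label suggests.

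A reader might infer more than the documents support in four ways.

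- **That a fifth of outcomes are wrongly preset (12% + 8.8% = 20.8%).** The resistant 8.8% should not be counted against the rule. Section 7.4 has another antibiotic started in these children, so most fail the endpoint anyway. A constant share of failures also scales the curve equally at every duration and cannot ease a relative 90% criterion.
- **That the rule flattens the curve to 79% of the microbiological-confirmed one.** The factor 0.792 arises from including children without a susceptible UTI, and it remains with observed outcomes if q is flat.
- **That the rule lowers the required cure rate in susceptible children from 85.5% to 84.0%** (10-day cure of 95% assumed). With observed outcomes and flat q of 0.95, 0.90 or 0.80, the requirement is 0.855 − 0.012q/0.792 = 84.1%, 84.1% or 84.3%. The rule itself accounts for only 0.1 to 0.3 of the 1.5 points.
- **That the stated 634 is wrong because the rules also classify children lost to follow-up.** Section 14.3 does not say that they do, and 634 is simply 705 less 10%.

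**Conclusion.** The point holds for the no-growth and below-threshold rules. They contradict the endpoint in Sections 8.1 and 14.4, override outcomes that Sections 9.1 and 9.6 plan to collect, and are not offset by any analysis named in Section 14.7. The affected share is at most about 12% of randomised children.

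The direction is towards shorter courses unless these children do better on shorter courses. The size is negligible if their outcomes do not depend on duration. If they do, it could reach about half a day on the assumed curves. That would matter only where it moves the recommended duration, since Section 14.4 takes the smallest duration above the upper confidence limit for D*. The 5% to 20% failure rate and all the cure curves are assumptions.

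The primary analysis on the microbiological-confirmed population is untouched, so this is a worthwhile correction to a secondary analysis and not a threat to the trial's main conclusion.

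**What to change.** In Section 14.3, base the ITT curve on the observed day-16 composite (fever and additional systemic antibiotic) for every randomised child, whatever the baseline culture showed. Handle missing outcomes as in the primary analysis, because about 10% loss to follow-up is expected and not every child will have the assessment. Keep the culture-based assignment as a labelled sensitivity analysis, and say there whether it extends to children lost to follow-up.

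The cost is a rewrite of Section 14.3 and the matching SAP text before outcomes are analysed. No new data are needed. The downside is small: in culture-negative children, fever or antibiotics from another illness will count as failures, and some children will have stopped cefalexin early under Section 7.4. Reporting both versions side by side shows how much this matters.

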14.4 Primary outcome

The primary outcome is clinical UTI cure rate, defined as patients in whom there is (i) fever resolution and (ii) no additional systemic antibiotic prescription by 16 days post-randomisation. A duration-response curve will be fitted using a fixed-2 fractional-polynomial model. This curve will then be analysed to obtain the optimal number of days (D*), such that the UTI cure rate preserves at least 90% of the efficacy provided by the maximum length (10 day) course of antibiotics. A confidence interval will be constructed around D* using bootstrapping methods and the smallest

duration that is greater than the upper end of the confidence interval, will be the recommended duration required (30). Figure 3 provides an example of a hypothetical curve and how the optimal duration will be calculated. This analysis will be performed for both the primary and ITT analysis cohorts as described in Sections 14.2 and 14.3.

Figure 3: Hypothetical duration-response curve

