3. TRIAL DESIGN AND SETTING

3.1 Trial design

A multi-centre, open label, multi-arm RCT using a "DURATIONS design," with an internal pilot and a within-trial cost effectiveness analysis. Participants will be randomised to one of five different durations of cefalexin treatment: 3, 5, 6, 8 and 10 days.

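### D* is the minimum duration that meets the 90% criterion, with no provision for a fitted curve that dips afterwards; for late-rising curves this pulls the upper limit, and so the recommendation, towards courses that are too short

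*Protocol*

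**What the plan says.** Protocol section 14.4 states the model: "A duration-response curve will be fitted using a fixed-2 fractional-polynomial model". From that curve it takes "the optimal number of days (D*), such that the UTI cure rate preserves at least 90% of the efficacy provided by the maximum length" course. It then says: "A confidence interval will be constructed around D* using bootstrapping methods". The recommended duration is the next one above the upper end of that interval.

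The Analysis paragraph of the trial summary says the curves will be used to "estimate the minimum duration of cefalexin, to ensure that at least 90% of the efficacy" of the 10-day course is achieved. Section 2.2.1 likewise glosses the optimal duration as the shortest effective one.

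Neither place states that the curve must rise with duration, or what happens if it crosses the 90% line more than once. The powers and the level and type of the bootstrap interval are not given either. Section 14.1 gives an operating characteristic for the curve (average absolute error) but none for D*. It says that power for D* depends on the curve's shape, and it asks the DMC to assess a more accurate simulation after the internal pilot.

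**The concern.** A two-term fractional polynomial can fall and then rise. A fitted or resampled curve may lie above the 90% line at 3 days, below it at 5-6 days, and above it again by 8-10 days. The minimum qualifying duration is then 3 days, although the same curve says that 5 and 6 days fail. A course length that qualifies only because of such a shape does not show that efficacy is preserved.

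Each bootstrap sample of this kind contributes a D* near 3 days and drags the upper percentile down. The error runs one way, towards courses that are too short, and it enters the primary decision rule. Section 1.1.2 itself warns that shortening treatment could raise total antibiotic use through re-treatment. Section 1.2.3 says that evidence on short courses is limited, so a late-rising curve cannot be ruled out beforehand.

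**Working it through.** **Inputs from the protocol.** Five arms: "Participants will be randomised to one of five different durations of cefalexin treatment: 3, 5, 6, 8 and 10 days" (section 3.1). Analysed patients: "We estimate that this will provide us with 500 patients (100 in each duration) for our microbiological population" (section 14.1). That figure reproduces: 500 / (0.88 × 0.90 × 0.90) = 701.5, against the stated 705, and 705 × 0.7128 = 502.5. The protocol gives no coverage figure for D* to reproduce.

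**Assumptions.** The protocol gives no cure rates, powers or interval level. The runs assume a logistic two-term model and a two-sided 95% percentile bootstrap, so the nominal chance that the upper limit falls below the true D* is 2.5%.

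**Two readings of D\*.** Rule A: the first duration with p(d) ≥ 0.9 × p(10). Rule B: the first duration from which p(d) ≥ 0.9 × p(10) holds at every d up to 10.

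**Late-rising true curves** (D* by linear interpolation between arms; a different interpolation gave 5.6, 5.4 and 5.8):

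| Curve | Cure % at 3/5/6/8/10 days | 90% line | Points below line at 3 and 5 days | True D* |
|---|---|---|---|---|
| a | 84/85/86/90/95 | 0.9 × 95 = 85.5 | 1.5, 0.5 | 5 + 0.5/1 = 5.5 |
| b | 85.5/86/87.5/94/96 | 0.9 × 96 = 86.4 | 0.9, 0.4 | 5 + 0.4/1.5 = 5.3 |
| c | 82/82/83/91/92 | 0.9 × 92 = 82.8 | 0.8, 0.8 | 5 + 0.8/1 = 5.8 |

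**Why dips occur.** Take curve a and the raw arms. The standard error at 3 days is √(0.84 × 0.16/100) = 3.7 points. The standard error of the line is 0.9 × √(0.95 × 0.05/100) = 2.0 points. For the difference it is √(3.67² + 1.96²) = 4.2 points. A true deficit of 1.5 points is 0.36 standard errors, so the 3-day arm lies above the line by chance in about 36% of trials. Smoothing reduces this but does not remove it.

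**Upper limit below the true D\*, % of trials:**

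| Model and runs | Curve | Rule A | Rule B |
|---|---|---|---|
| Fixed powers (0.5,2), (-2,1), (-1,3); 1,500 trials × 400 resamples | a | 6.3-10.9 | 2.0-3.7 |
| | b | 7.9-9.4 | 3.1-3.6 |
| | c | 6.1-7.9 | 3.1-3.8 |
| Same powers, linear interpolation; 1,000 × 400 | a | 7.0-12.4 | 2.6-3.7 |
| | b | 6.0-7.7 | 2.1-3.6 |
| | c | 5.1-7.7 | 2.4-3.9 |
| Five fixed power pairs | a-c | 5-17 | 1.5-7 |
| Powers chosen by likelihood from 36 pairs; 1,500 × 500 | late rise 84 to 95%, middle at day 7 | 9.6 | 4.9 |
| | late rise 80 to 92%, middle at day 8 | 16.3 | 8.6 |

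The Monte Carlo standard error with 1,500 trials is √(0.025 × 0.975/1500) = 0.4 points at 2.5% and √(0.08 × 0.92/1500) = 0.7 points at 8%.

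**Effect on the recommendation.** For curves a-c, an arm that truly fails the criterion was recommended in 2-10% of trials under Rule A and 0.3-3% under Rule B (five power pairs). Fitted curves dipped in 12-36% of these trials. For the two likelihood-chosen late-rise cases, a whole-day recommendation below the true D* fell from 8.0% to 3.3% (middle at day 7) and from 10.5% to 3.7% (middle at day 8).

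**Other shapes** (powers chosen by likelihood, Rule A then Rule B):

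- Saturating, logit-linear and logit-log: 2.0-3.4% then 1.8-2.6%.
- Shallow linear: 3.5-3.7% then 1.0-1.3%.
- Linear 70 to 95%: 7.2% then 7.1%.
- Kinked with a plateau from day 6: 9.4-10.3% then 9.1-9.3%.
- Sigmoid 80 to 95%, middle at day 5: 10.1% then 9.2%.
- Accelerating 75 to 95%: 11.4% then 11.0%.
- Flat: 0% under both.

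Of 22 curves tried, 15 had a Rule A miss below twice nominal (0-3.7%).

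**The case against.** The strongest reply is that the protocol nowhere says first crossing. A minimum duration meant to guarantee 90% efficacy could be read as Rule B, and section 1.2.2 speaks of the curve flattening off, which suggests that the authors had a rising curve in mind. Section 14 calls itself a brief overview and defers to a separate SAP. Section 14.4 also points to Figure 3 and a cited methods paper for the calculation; neither could be read for this review.

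Part of this stands. The SAP or the figure may already settle the matter, and missing detail on powers or bootstrap type is no fault of a protocol. But the protocol does fix the target and the decision rule in words, and the ordinary sense of a minimum qualifying duration is Rule A. If Rule B is intended, the wording should say so.

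A reader might also infer that the interval generally misses two to four times too often, or that ignored dips explain every excess miss. The runs do not support either reading. Most curves are near nominal, and for kinked, steep and accelerating curves Rule B moves the miss rate by about a point or less.

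Nor do the scenarios show large clinical harm. In curves a-c the failing arms lie at most 1.5 points below a line that already concedes 9.2-9.6 points, and the 6-day arm passes in all three. Rounding up to the next duration also makes a wrong recommendation rarer than a missed upper limit.

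**Conclusion.** The point holds in a limited form. As worded, D* ignores a later dip of the same fitted curve below the 90% line, and this biases the bootstrap upper limit towards durations that are too short. For late-rising curves the upper limit falls below the true D* in about 5-17% of trials against 2.5% nominal; counting the dip roughly halves this or does better, to about 1.5-9%. For early-rising, saturating curves the choice hardly matters. Elsewhere most of the excess miss is misfit and would remain.

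These figures rest on an assumed 95% percentile interval, assumed powers and assumed cure rates; only the arms and the 100 per arm come from the protocol. The direction is the same with fixed and with likelihood-chosen powers. It is a change worth making before analysis, not a flaw that undermines the design.

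**What to change.** In section 14.4 and the summary, define D* as the smallest duration at which, and at every longer duration up to 10 days, the fitted cure rate is at least 90% of the fitted 10-day rate. Apply the same definition in every bootstrap sample, and carry the wording into the SAP. Ask that the DMC simulation promised in section 14.1 report how often the upper limit falls below the true D*, with late-rising, kinked and accelerating curves among its scenarios, since the new definition does not cure misfit.

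The cost is one sentence and one line of code. Recommendations become somewhat longer: on average by about 0.1-0.45 days for the late-rising curves a-c, and by 0.4-0.8 days if the true curve is flat.

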1.2.3 Justification for choice of interventions

Cefalexin, a first-generation cephalosporin, is the recommended first-line oral antibiotic for febrile UTIs in England (9, 10). Children taking part in the CURLY trial will be randomised to one of five cefalexin course durations. The number of arms chosen is in accordance with the employed "DURATIONS design" (29, 30).

Justification for shortest and longest treatment lengths

Evidence on short course efficacy to inform the duration of the shortest treatment is limited. Treatment of **3 days** is standard practice for UTIs in adults (31). This duration has been selected for our shortest treatment arm, following a consultation survey with clinical representatives from 58 paediatric EDs. The survey identified that a small number of EDs currently deviate from national guidance and prescribe 3-day antibiotic courses for children with febrile UTIs. The longest treatment duration of **10 days** is in line with the maximum duration suggested by the NICE guideline (9).

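### The recommendation rule uses a strict inequality: with D* searched over 3 to 10 days it cannot return the 3-day arm, and an upper limit of 10 gives no result

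*Protocol*

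**What the plan says.** Section 14.4 of the protocol fits a fixed-2 fractional polynomial to cure against duration and reads off D*, "such that the UTI cure rate preserves at least 90% of the efficacy provided by the maximum length (10 day) course". The Trial Summary makes clear that the target is a minimum: "These curves will then be used to estimate the minimum duration of cefalexin".

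The step from curve to conclusion, also in Section 14.4, is a single sentence. Once a bootstrap interval for D* has been built, the lowest "duration that is greater than the upper end of the confidence interval, will be the recommended duration required".

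The range of data is set by the arms. Section 3.1 says: "Participants will be randomised to one of five different durations of cefalexin treatment: 3, 5, 6, 8 and 10 days". Section 1.2.3 explains both ends. Of 3 days it says: "This duration has been selected for our shortest treatment arm". Of the other end it says: "The longest treatment duration of 10 days is in line with the maximum duration suggested by the NICE guideline".

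Section 2.2.1 names the shortest effective duration as the primary objective. No other section restates the recommendation rule in different words.

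**The concern.** This sentence turns the fitted curve into the trial's answer, so its behaviour at the ends of the range matters. The shortest arm was chosen deliberately. A flat curve is the result most favourable to shortening treatment, and it pushes both D* and its upper limit down to 3. A rule that demands a duration greater than that limit then passes over 3 days and names 5 (the next arm) or 4 (the next whole day). The trial could gather the strongest evidence its design allows for the 3-day arm and be barred by wording from reporting it as the recommendation. At the other end, an upper limit of 10 leaves no studied duration that is greater.

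**Working it through.** **Inputs from the protocol.** Arms of 3, 5, 6, 8 and 10 days (3.1); criterion cure(D) ≥ 0.90 × cure(10) (14.4); recommended duration > U, where U is the upper limit for D* (14.4); 100 per arm in the microbiological-confirmed population (14.1).

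**Assumed, because the protocol does not give them.** True cure rates; confidence level (97.5th percentile used for U); percentile bootstrap; search range and step for D*; powers of the second-degree polynomial chosen by best fit.

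**1. The plan's own figures.** 500 / (0.88 × 0.90 × 0.90) = 500 / 0.7128 = 701.5, and 705 × 0.7128 = 502.5, so 705 delivers the 500 required. 705 × 0.90 = 634.5 (634 stated). The sample size is not in dispute, and 100 per arm is used below.

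**2. Lower end, by logic.** Search D* over 3 to 10 days. Every bootstrap D* is then at least 3, so U ≥ 3, and the smallest duration with d > U is above 3. When U = 3 exactly, at least 97.5% of resamples satisfy cure(3) ≥ 0.90 × cure(10). So 3 days meets the protocol's criterion at the chosen confidence, and the strict rule still rejects it.

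**3. How often U = 3.** For a flat curve cure(3) = cure(10), so the true D* on the studied range is 3. For a mild curve from 90% to 95%, 0.90 × 95% = 85.5%, which is below 90%, so the true D* is again 3. Share of trials with U exactly 3 in three separately written simulations:

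| Assumed cure | A (200 trials, 300 resamples) | B (200 trials, 200 resamples) | C |
|---|---|---|---|
| Flat 95% | 185/200 = 92.5% | 87% | about 88% |
| Flat 90% | 131/200 = 65.5% | 60% | about 72% |
| Flat 85% | 107/200 = 53.5% | 44% | not available |
| Mild, 90% to 95% | 60/200 = 30% | 25% | about 26% |

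In A, the strict rule chose 3 days in 0/200 trials in all four rows. With equality allowed it chose 3 days in exactly the counts shown. Simulation error is not negligible: at 65.5%, √(0.655 × 0.345 / 200) = 3.4 percentage points. Further runs under nominally similar settings gave lower shares (65% and 69% at flat 95%; 35% and 26% at flat 90%). A, B and C did not reproduce these, and they are not relied on. They do show that the percentages give an order of size only.

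For a curve rising from 80% to 95%, 3 days fails the criterion (80% is below 85.5%) and U = 3 occurred in 0% of trials. The defect therefore bites when the curve is flat or nearly so.

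**4. If the curve is extrapolated below 3 days.** Searching from 1 to 10 days, U fell below 3 in 89%, 68% and 57% of trials (flat 95%, 90%, 85%). The strict rule could then return 3; at flat 90% it did so in 135/200 trials.

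**5. Upper end.** On a continuous curve, 0.90 × cure(10) is below cure(10), so the criterion is already met just short of 10 days. Every D* is below 10, and a percentile limit cannot reach 10. With a late steep rise (70% at 3, 5 and 6 days, 75% at 8, 95% at 10) the largest U was 9.40. With a whole-day search on the same curve, U = 10 in 132/200 = 66% of trials and the strict rule returned nothing. It was 0% in the other scenarios. An interval not bounded at 10 could also get there; that was not simulated.

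**The case against.** Section 14 describes itself as an overview and leaves detail to a SAP that was not available. Section 14.4 cites a methods paper for the rule and points to Figure 3 for an example, which could not be seen in the text reviewed. Search range, step, interval type and confidence level are ordinary SAP content, and their absence is no fault. The wording may simply be loose shorthand for the cited method. Moving from 3 to the next day or arm is a modest shift, and an interval collapsed onto 3 would be visible in any report.

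Most of that is fair, and it limits the point. A reader might infer that 3 days can never be recommended on any reading. The protocol does not support that: it does not confine D* to 3 to 10 days, and if the curve is extrapolated below 3 with the five arms as candidates, the rule can return 3. A reader might also put the 10-day gap on the same footing as the 3-day one. It is a corner case, out of reach with a continuous search and a percentile interval.

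What the objection does not remove is that the protocol states the inequality, and states it as strict. A SAP that follows the text faithfully inherits it. Extrapolation is a poor rescue, because the fate of the 3-day arm would rest on a part of the curve where no child was randomised. A visible interval does not help if the prespecified rule names another duration.

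**Conclusion.** The point holds conditionally. If D* is searched within the studied 3 to 10 days and the limit is a percentile bootstrap limit, the rule as worded cannot return the 3-day arm; that part is logic and needs no simulation. The boundary is an ordinary result and not a rarity: with 100 per arm and assumed flat cure rates of 90% to 95%, it is reached in roughly two-thirds to nine-tenths of simulated trials, and in about a quarter to 30% for a mild rise from 90% to 95%. Those shares depend on cure rates, interval type and fitting choices that the protocol does not give. The missing result at an upper limit of 10 is real but secondary. Because the sentence governs the primary conclusion and conflicts with the objective in Section 2.2.1, it should be corrected, although outcome, data collection and sample size are untouched.

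**What to change.** In Section 14.4, and in the SAP to match, state three things:

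- D* is searched for only within 3 to 10 days.
- The recommended duration is the shortest candidate duration equal to or greater than the upper confidence limit for D*.
- Candidates are either the five randomised arms or any whole day from 3 to 10. The second option allows 4, 7 and 9 days, which no arm receives, so the choice should be made openly.

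A limit of 3 then returns 3 and a limit of 10 returns 10. If the SAP uses an interval that can exceed 10, it should also say how such a limit is handled.

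The cost is one sentence, with no new data and no change to 705. Make the change before any outcome data by arm are analysed, and preferably before the end-of-pilot simulation that Section 14.1 assigns to the DMC, so that it tests the rule that will be used. Changing the inequality after an upper limit of 3 has been seen would look data-driven. The change concerns the statistical rule alone and implies no view on which duration is clinically right.
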